## **8.2 Treatment of Avelumab Related Infusion Reactions**

### A. Symptoms

- ξ Fever
- ξ Chills
- ξ Rigors
- ξ Diaphoresis
- ξ Headache

### B. Management

**Table 1 Treatment Modification for Symptoms of Infusion-Related Reactions**

NCI-CTCAE Grade	Treatment Modification for Study Drug
Grade 1 – mild Mild transient reaction; infusion interruption not indicated; intervention not indicated.	Decrease the study drug infusion rate by 50% and monitor closely for any worsening. The total infusion time for study drug should not exceed 120 minutes.
Grade 2 – moderate Therapy or infusion interruption indicated but responds promptly to symptomatic treatment (for example, antihistamines, NSAIDs, narcotics, IV fluids); prophylactic medications indicated for $\delta$ 24 h.	Stop study drug infusion. Resume infusion at 50% of previous rate once infusion-related reaction has resolved or decreased to at least Grade 1 in severity, and monitor closely for any worsening.
Grade 3 or Grade 4 – severe or life-threatening Grade 3: Prolonged (for example, not rapidly responsive to symptomatic medication and/or brief interruption of infusion); recurrence of symptoms following initial improvement; hospitalization indicated for clinical sequelae. Grade 4: Life-threatening consequences; urgent intervention indicated.	Stop the study drug infusion immediately and disconnect infusion tubing from the subject. Subjects have to be withdrawn immediately from study drug treatment and must not receive any further study drug treatment.

IV = intravenous; NCI-CTCAE = National Cancer Institute-Common Terminology Criteria for Adverse Event; NSAIDs = nonsteroidal anti-inflammatory drugs.

Once the avelumab infusion rate has been decreased by 50% or interrupted due to an infusion-related reaction, it must remain decreased for all subsequent infusions. If the subject has a second infusion-related reaction Grade  $\geq 2$  on the slower infusion rate, the infusion should be stopped and the subject should be removed from study treatment. If a subject experiences a Grade 3 or 4 infusion-related reaction at any time, the subject must discontinue study drug. No Avelumab dose reductions are permitted on this study. Patients who experience grade IV toxicity will continue to be followed until toxicity resolution to Grade  $\leq 1$  or return to baseline.

### ***Severe Hypersensitivity Reactions and Flu-Like Symptoms***

If hypersensitivity reaction occurs, the subject must be treated according to the best available medical practice. Subjects should be instructed to report any delayed reactions to the Investigator immediately.

[figure not shown]
For prophylaxis of flu-like symptoms, 25 mg of indomethacin or comparable nonsteroidal anti-inflammatory drug (NSAID) dose (for example, ibuprofen 600 mg, naproxen sodium 500 mg) may be administered 2 hours before and 8 hours after the start of each dose of avelumab IV infusion. Alternative treatments for fever (for example, paracetamol) may be given to subjects at the discretion of the Investigator.

### ***Tumor Lysis Syndrome***

In addition, since avelumab can induce antibody-dependent cell-mediated cytotoxicity, there is a potential risk of tumor lysis syndrome. Should this occur, subjects should be treated per the local guidelines and the management algorithm below ([Howard 2011](#)).

### Assessment and Initial Management of Tumor Lysis Syndrome

TLS = tumor lysis syndrome

### **Immune-Related Adverse Events**

Since inhibition of PD-L1 stimulates the immune system, immune-related AEs (irAEs) may occur. Treatment of irAEs is mainly dependent upon severity (NCI-CTCAE grade):

Grade 1 to 2: treat symptomatically or with moderate dose steroids, more frequent monitoring

Grade 1 to 2 (persistent): manage similar to high grade AE (Grade 3 to 4)

Grade 3 to 4: treat with high dose corticosteroids

Treatment of irAEs should follow guidelines set forth in the table below Table.

**Table 2 Management of Immune-Related Adverse Events**

Gastrointestinal irAEs		
Severity of Diarrhea / Colitis (NCI-CTCAE v4.03)	Management	Follow-up
Grade 1 Diarrhea: < 4 stools/day over Baseline Colitis: asymptomatic	Continue avelumab therapy Symptomatic treatment (for example, loperamide)	Close monitoring for worsening symptoms Educate subject to report worsening immediately If worsens: Treat as Grade 2 or 3/4
Grade 2 Diarrhea: 4 to 6 stools per day over Baseline; IV fluids indicated < 24 hours; not interfering with ADL Colitis: abdominal pain; blood in stool	Delay avelumab therapy Symptomatic treatment	If improves to Grade 1: Resume avelumab therapy If persists > 5 to 7 days or recur: 0.5 to 1.0 mg/kg/day methylprednisolone or equivalent When symptoms improve to Grade 1, taper steroids over at least 1 month, consider prophylactic antibiotics for opportunistic infections, and resume avelumab therapy per protocol. If worsens or persists > 3 to 5 days with oral steroids: Treat as Grade 3 to 4
Grade 3 to 4 Diarrhea (Grade 3): ≥ 7 stools per day over Baseline; incontinence; IV fluids ≥ 24 hrs; interfering with ADL Colitis (Grade 3): severe abdominal pain, medical intervention indicated, peritoneal signs Grade 4: life-threatening, perforation	Discontinue avelumab therapy per protocol 1.0 to 2.0 mg/kg/day methylprednisolone IV or equivalent Add prophylactic antibiotics for opportunistic infections Consider lower endoscopy	If improves: Continue steroids until Grade 1, then taper over at least 1 month If persists > 3 to 5 days, or recurs after improvement: Add infliximab 5 mg/kg (if no contraindication), Note: Infliximab should not be used in cases of perforation or sepsis

Dermatological irAEs		
Grade of Rash (NCI-CTCAE v4)	Management	Follow-up
Grade 1 to 2 Covering ≤ 30% body surface area	Symptomatic therapy (for example, antihistamines, topical steroids) Continue avelumab therapy	If persists > 1 to 2 weeks or recurs: Consider skin biopsy Delay avelumab therapy Consider 0.5 to 1.0 mg/kg/day methylprednisolone IV or oral equivalent. Once improving, taper steroids over at least 1 month, consider prophylactic antibiotics for opportunistic infections, and resume avelumab therapy If worsens: Treat as Grade 3 to 4
Grade 3 to 4 Covering > 30% body surface area; life threatening consequences	Delay or discontinue avelumab therapy Consider skin biopsy Dermatology consult 1.0 to 2.0 mg/kg/day methylprednisolone IV or IV equivalent	If improves to Grade 1: Taper steroids over at least 1 month and add prophylactic antibiotics for opportunistic infections Resume avelumab therapy
Pulmonary irAEs		
Grade of Pneumonitis (NCI-CTCAE v4)	Management	Follow-up
Grade 1 Radiographic changes only	Consider delay of avelumab therapy Monitor for symptoms every 2 to 3 days Consider Pulmonary and Infectious Disease consults	Re-image at least every 3 weeks If worsens: Treat as Grade 2 or Grade 3 to 4
Grade 2 Mild to moderate new symptoms	Delay avelumab therapy Pulmonary and Infectious Disease consults Monitor symptoms daily, consider hospitalization 1.0 mg/kg/day methylprednisolone IV or oral equivalent Consider bronchoscopy, lung biopsy	Re-image every 1 to 3 days If improves: When symptoms return to near Baseline, taper steroids over at least 1 month and then resume avelumab therapy and consider prophylactic antibiotics If not improving after 2 weeks or worsening: Treat as Grade 3 to 4
Grade 3 to 4 Severe new symptoms; New / worsening hypoxia; life-threatening	Discontinue avelumab therapy Hospitalize Pulmonary and Infectious Disease consults	If improves to Baseline: Taper steroids over at least 6 weeks If not improving after 48 hours or worsening:

	2 to 4 mg/kg/day methylprednisolone IV or IV equivalent Add prophylactic antibiotics for opportunistic infections Consider bronchoscopy, lung biopsy	Add additional immunosuppression (for example, infliximab, cyclophosphamide, IV immunoglobulin, or mycophenolate mofetil)
Hepatic irAEs		
Grade of Liver Test Elevation (NCI-CTCAE v4)	Management	Follow-up
Grade 1 Grade 1 AST or ALT > ULN to 3.0 x ULN and / or total bilirubin > ULN to 1.5 x ULN	Continue avelumab therapy	Continue liver function monitoring If worsens: Treat as Grade 2 or 3 to 4
Grade 2 AST or ALT > 3.0 to ≤ 5 x ULN and / or total bilirubin > 1.5 to ≤ 3 x ULN	Delay avelumab therapy Increase frequency of monitoring to every 3 days	If returns to Baseline: Resume routine monitoring, resume avelumab therapy If elevations persist > 5 to 7 days or worsen: 0.5 to 1 mg/kg/day methylprednisolone or oral equivalent and when LFT returns to Grade 1 or Baseline, taper steroids over at least 1 month, consider prophylactic antibiotics for opportunistic infections, and resume avelumab therapy
Grade 3 to 4 AST or ALT > 5 x ULN and / or total bilirubin > 3 x ULN	Discontinue avelumab therapy Increase frequency of monitoring to every 1 to 2 days 1.0 to 2.0 mg/kg/day methylprednisolone IV or IV equivalent Add prophylactic antibiotics for opportunistic infections Consult gastroenterologist Consider obtaining MRI/CT scan of liver and liver biopsy if clinically warranted	If returns to Grade 2: Taper steroids over at least 1 month If does not improve in > 3 to 5 days, worsens or rebounds: Add mycophenolate mofetil 1 gram (g) twice daily If no response within an additional 3 to 5 days, consider other immunosuppressants per local guidelines
Endocrine irAEs		
Endocrine Disorder	Management	Follow-up
Asymptomatic TSH abnormality	Continue avelumab therapy If TSH < 0.5 x LLN, or TSH > 2 x ULN, or consistently out of range in 2 subsequent measurements: include T4 at subsequent cycles as clinically indicated; consider endocrinology consult	
Symptomatic endocrinopathy	Evaluate endocrine function Consider pituitary scan Symptomatic with abnormal lab / pituitary scan:	If improves (with or without hormone replacement):

	Delay avelumab therapy 1 to 2 mg/kg/day methylprednisolone IV or by mouth equivalent Initiate appropriate hormone therapy No abnormal lab / pituitary MRI scan but symptoms persist: Repeat labs in 1 to 3 weeks / MRI in 1 month	Taper steroids over at least 1 month and consider prophylactic antibiotics for opportunistic infections Resume avelumab therapy Subjects with adrenal insufficiency may need to continue steroids with mineralocorticoid component
Suspicion of adrenal crisis (for example, severe dehydration, hypotension, shock out of proportion to current illness)	Delay or discontinue avelumab therapy Rule out sepsis Stress dose of IV steroids with mineralocorticoid activity IV fluids Consult endocrinologist If adrenal crisis ruled out, then treat as above for symptomatic endocrinopathy	

ADL = activities of daily living; ALT = alanine aminotransferase; AST = aspartate aminotransferase; CT = computed tomography; irAE = immune-related adverse event; IV=intravenous; LFT = liver function test; LLN = lower limit of normal; MRI = magnetic resonance imaging; NCI-CTCAE = National Cancer Institute-Common Terminology Criteria for Adverse Event; T4 = free thyroxine; TSH = thyroid-stimulating hormone; ULN = upper limit of normal.

## 9. CORRELATIVE/SPECIAL STUDIES (Section applicable to UCSD site only)

### 9.1 Specimen handling and storage

- 9.1.1 Patient samples collected for this study will be retained in the laboratory of [name] for analysis and future cancer research. Specimens will be stored indefinitely or until there is no remaining sample available. If future use is denied or withdrawn by the patient, best efforts will be made to stop any additional studies and to destroy the specimens. Samples will be labeled with the protocol number, subject's de-identified study number and collection date.
- 9.1.2 The following information obtained from the subject's medical record may be provided to research collaborators when specimens are made available:
- Diagnosis
  - Collection time in relation to study treatment
  - Clinical outcome – if available
  - Demographic data
- 9.1.3 The study coordinator or research staff will transport the specimen to the laboratory of [name]., PhD for storage and processing.
- 9.1.4 Specimen will be labeled with the protocol number, subject's de-identified study number and collection date.
- 9.1.5 The samples will be centrifuged within 45 minutes of collection and plasma and peripheral blood mononuclear cells will be processed and stored at -80°C for future analysis.

### 9.2 Methodology

- 9.2.1 80cc Blood samples will be collected from patients into sodium heparin coated vacutainers (BD Vacutainer® Green BD Hemogard™) at time points specified under the study protocol. PBMC and Serum will be isolated via standard Ficoll gradient centrifugation.
- 9.2.2 We will perform Multiparametric Flow cytometry and additional immunologic assays on peripheral mononuclear cells (PBMC) from patient derived blood samples to quantify changes in T-cell and B-cell activation and proliferation before, during and after SBRT combined with Avelumab: T-cell subsets (CD3, CD4, CD8, CD25, FOXP3, CD69, CD44, CD62L, PD-1, IFN-gamma, TNF-alpha), B cells (CD19, CD20), Macrophage I/II and myeloid-derived suppressor cells (MDSC) (CD16, CD68, CD206) and Natural killer cell activity (CD56, CD16).
- 9.2.3 We will perform Next generation sequencing including T-cell receptor sequencing (ImmunoSeq), using TCR-Beta CDR3 Kit (Adaptive Biotechnologies). TCR-β CDR3, regions will be amplified and sequenced using the survey ImmunoSeq assay in a multiplexed PCR method.
- 9.2.4 Assessment of humoral immune responses will be performed using high-content protein microarray. Candidate antigens will be verified using multiplexed antigen-conjugated, spectrally distinguishable, fluorescent proprietary microspheres

### **9.3 Correlative Study Endpoints:**

- 9.3.1 Statistical and Graphical analyses will be performed in the "R" computing environment, Prism (GraphPad), and FlowJo (FlowJo, LLC).
- 9.3.2 For ImmunoSeq Analysis: Shannon entropy will be calculated on the clonal abundance of all productive TCR and BCR sequences in the data set. This normalized entropy value will then inverted ( $1 - \text{normalized entropy}$ ) to produce the clonality metric.
- 9.3.3 For analytical assessment of serum anti-tumor immune responses: changes in serum antibody levels will be reported relative to pretreatment. To assess the statistical significance of pre- to post-treatment changes in levels of IgGs, normalized signal intensities ( $\log_2$ ) will be tested using a moderated paired t test.

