### **6.3.2 SBRT Procedures**

Upon enrollment on the protocol patients will be seen by at least one of the Co-Investigator Medical Oncologists. As per standard of care a 4D CT simulation will be performed with fabrication of a radiation therapy immobilization device (such as a Vac-Lok) which will be custom made for each patient. The treating radiation oncologist will identify the location of the tumor. Gross tumor volume (GTV) delineation will be performed on sequential axial computed tomography images. An SBRT treatment plan will be developed based on tumor size and location. The radiation dose will be prescribed using the current clinical practice standard of care of either 12Gy x 4 fractions or 10Gy x 5 fractions at the discretion of the treating radiation oncologist.

Adjacent normal structures including but not limited to the chest wall, spinal cord, lung, airways at risk, vessels at risk, heart, esophagus, aorta, liver, and stomach within 5 cm of the GTV will be identified for the purpose of limiting incidental radiation to these structures.

The patient will receive the first fraction of SBRT within 3-10 days after starting the 1st cycle of Avelumab. SBRT will be administered using image-guidance as per standard of care. An Vac-Lok (or equivalent immobilization device such as Alpha-Cradle) will be used to minimize movement of the chest, spine, and abdomen during treatment. During treatment, cone beam images of the patient's body site of interest will be obtained. Cone beam scan will be obtained immediately prior to treatment and will be repeated until the treatment shift, required to align the Radiation planning scan and the cone beam scan performed on the day of treatment. Cone beam scanning is standard of care for definitive stereotactic body radiation therapy.

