### 15.5 Analysis of Secondary Objectives

- To determine whether SBRT combined with concurrent and adjuvant Avelumab results in improved loco-regional control, relapse free survival, and overall survival we will evaluate the recist criterion scans and survival rates at 6 months, 12 months and 24 months.
- To analyze whether SBRT combined with concurrent and adjuvant Avelumab impacts anti-tumor immune responses we will perform immunologic assays quantifying lymphocyte specificity and activation, including Immune cell Sequencing, ProtoArrays, Immunoassays, cell free DNA analyses, and multiparametric flow cytometry.
- Hazard rate estimates and 95% confidence intervals as well as Kaplan-Meier (KM) estimates will be used to summarize survival (OS), progression free survival (RFS), time to locoregional progression (TTLP) and time to distant progression (TTDP),

duration of response functions over time, and stable disease (SD). The median OS, PFS, TTLP, TTDP, and SD will be reported.

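### Section 9.3.2 computes clonality without fixing the entropy divisor or equalising template counts, so a difference in sequencing yield between draws can pass for, hide or reverse a change in the repertoire

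*Combined protocol and SAP*

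**What the plan says.** Section 9.3.2 defines the metric in two steps. First, "Shannon entropy will be calculated on the clonal abundance of all productive TCR and BCR sequences in the data set". Second, "This normalized entropy value will then inverted", that is, clonality is 1 minus normalised entropy. The quantity used to normalise is not given. I read the data set as one blood sample, since a pooled value could not show change over time.

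On input, Section 9.2.1 fixes only the volume of blood: "80cc Blood samples will be collected from patients into sodium heparin coated vacutainers". Section 9.2.3 names the assay ("regions will be amplified and sequenced using the survey ImmunoSeq assay in a multiplexed PCR method") but no DNA mass, cell number, target template count or minimum yield. Section 15.5 lists the sequencing among the assays for the immune objective ("we will perform immunologic assays quantifying lymphocyte specificity and activation, including Immune cell Sequencing, ProtoArrays, Immunoassays") and adds no depth adjustment.

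On timing, Section 9.2.2 speaks of changes "before, during and after SBRT combined with Avelumab". The study calendar (Section 10) marks research draws at pre-treatment and Cycle 3 Day 1, both optional. The synopsis mentions three draws.

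**The concern.** Clonality is the only T-cell receptor measure for which the plan gives a formula, and it serves objective 3.2.3. Its use lies in comparing a patient's later sample with the pre-treatment one. Indices built on entropy and observed richness are not depth-free: a sample holding only a small part of a large repertoire gives a different value if more or fewer templates are read from the same blood. Each draw is analysed at whatever depth it yields, so the before-and-after difference mixes biology with yield, and nothing in the plan separates the two.

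**Working it through.** **No plan figure to reproduce.** The documents state no expected clonality, template count, power or threshold for this endpoint. The check asks whether the index, computed as written, moves when only the template count changes.

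**Does the comparison span SBRT?** The first fraction falls 3 to 10 days after Cycle 1 starts (Section 6.3.2), and 4 or 5 fractions are given every other day (Section 6.5). The last fraction is therefore between day 3 + 3×2 = 9 and day 10 + 4×2 = 18. Cycle 3 Day 1 is 2×14 = 28 days after Cycle 1 Day 1, which is 28 − 18 = 10 to 28 − 9 = 19 days after the last fraction if cycles run on time. The two calendar draws lie on either side of SBRT.

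**Formula.** With N templates, clone counts n_i and f_i = n_i/N, H = −Σ f_i ln f_i and clonality C = 1 − H/D. The divisor D is not stated. The candidates tried were ln(observed unique clones), ln(N) and a constant.

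**Why depth matters.** The expected share of templates that are singletons is Σ p_i(1 − p_i)^(N−1), which rises as N falls. In the limit where every template is a singleton, H = ln N, the number of observed clones is N, and C = 0 with D = ln(observed clones), whatever the true repertoire. The cause is not that sampling spares large clones: halving N halves every clone's expected count. With a constant divisor the direction differs. Since H cannot exceed ln N, C is at least 1 − ln N/D. For D = ln(1,000,000) that floor is 1 − 11.513/13.816 = 0.167 at N = 100,000 and 1 − 10.820/13.816 = 0.217 at N = 50,000.

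**Simulation.** Each repertoire was held fixed and sampled multinomially, 20 replicates per depth, with D = ln(observed unique clones). Repertoire shapes, sizes and depths are assumptions; none is in the documents.

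| Assumed repertoire | 100,000 | 50,000 | 25,000 | 100,000 to 50,000 |
|---|---|---|---|---|
| Power law 0.6, 1,000,000 clones | 0.0109 | 0.0074 | 0.0048 | −32% |
| Power law 0.8, 1,000,000 clones | 0.0579 | 0.0473 | 0.0381 | −18% |
| Power law 1.0, 1,000,000 clones | 0.2067 | 0.1872 | 0.1669 | −9% |
| 1,000,000 clones, 100 expanded holding 20% | 0.0914 | 0.0841 | 0.0763 | −8% |
| 1,000,000 clones, one holding 50% | 0.4368 | 0.4316 | 0.4254 | −1% |
| Power law 1.0, 2,000 clones | 0.2611 | 0.2617 | 0.2588 | +0.2% |
| Power law 0.6, 2,000 clones | 0.0575 | 0.0592 | 0.0616 | +3% |

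Across ten repertoires of 1,000,000 clones, this halving lowered the index by about 1% to 32%. For power law 1.0 the shift is 0.2067 − 0.1872 = 0.0195, against a replicate SD of about 0.001.

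**Other divisors.** For power law 1.0 from 100,000 to 50,000 templates, D = ln(N) gives 0.274 to 0.252 (a fall), and D = ln(1,000,000) gives 0.396 to 0.414 (a rise).

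**Can it reverse a real change?** Take 100,000 memory clones (power law 1.0) holding half the cells, the rest unique, with D = ln(observed unique clones). Raising the relative weight of the top 20 clones by 20% moves clonality from 0.1255 to 0.1349 when both samples have 200,000 templates, a rise of 0.0094. If the second sample yields 100,000 it reads 0.1225, an apparent fall of 0.0030. At 100,000 in both samples the values are 0.113 and 0.1225, and the rise of 0.0095 is recovered.

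**Does equalising work?** Samples of 100,000, 50,000 and 25,000 templates, each brought to 25,000, give 0.167, 0.167 and 0.167 for power law 1.0, and 0.038, 0.038 and 0.038 for power law 0.8. Simpson-type clonality in the 100,000-memory-clone model stayed near 0.053 from 200,000 to 25,000 templates.

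**The case against.** A reader might infer that SBRT will lower T-cell counts and that the trial will therefore report a spurious loss of clonality. The documents do not support this. They report no T-cell change after SBRT, and they do not say that sequenced templates follow the blood T-cell count. If a standard DNA mass is sequenced, yield follows the T-cell share of the mononuclear cells rather than the absolute count. The sign also depends on a divisor that Section 9.3.2 leaves open: a fixed one turns the fall into a rise.

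Four further objections deserve weight. Input and depth may be set in a kit procedure or laboratory manual outside these documents. The size comes from assumed repertoires, and with about 2,000 clones the problem almost disappears or changes sign. The before, during and after wording in Section 9.2.2 is attached to flow cytometry and additional assays; Section 9.2.3, on sequencing, has no timing of its own. Finally, no test or decision rests on clonality (the paired test in Section 9.3.3 concerns IgG), and down-sampling can still be done after the data are in.

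These points limit direction, size and consequence. They do not remove the dependence on depth, which arises from unequal yield of any cause, and the written rule uses all productive sequences. Settling the rule beforehand also avoids choosing a divisor or depth after seeing the results.

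**Conclusion.** The point holds as a minor, inexpensive improvement. As written, the clonality index is undefined in its divisor and depends on template count whenever the repertoire is much larger than the sample. That under-sampling is assumed for blood, not shown in the documents. With the log of observed unique clones as divisor, the assumed large repertoires give a fall of roughly 1% to 32% when templates are halved from 100,000. The size and direction in this trial cannot be stated, because yields, DNA or cell input and any T-cell change are not given. Only one correlative assay for objective 3.2.3 is affected, at the UCSD site and on optional draws. RFS and the safety rules are untouched.

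**What to change.** In Section 9.3.2:

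- State the divisor, for example the log of observed unique clones.
- Before computing clonality, down-sample each patient's serial samples to the smallest productive-template count among them, and average over repeated draws (say 100).
- Report the template count for every draw, and state a minimum yield below which a sample is not used, so that one poor sample does not pull the others to a very low depth.
- Give a Simpson-type clonality, which changes little with depth, as a sensitivity analysis.

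The cost is a few lines of analysis code; samples, assay and schedule stay as they are. The downside is slightly more sampling noise in the deeper samples: for power law 1.0 the replicate SD is 0.0008 at 100,000 templates and 0.0016 at 25,000, small beside the shift of 0.2067 − 0.1669 = 0.0398 between those depths.
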